2.3.3 Exploratory endpoints

Additional exploratory outcomes will be detailed in the Statistical Analysis Plan.

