2.7 Data analyses

Summary statistics will be calculated for all study endpoints. Categorical variables will be summarized using frequency distributions and continuous variables will be summarized with means and standard deviations (normal distributions) or medians and ranges (non-normal distributions). Confidence intervals (95% CI) may be computed for select study endpoint measures. The primary efficacy endpoint will be tested at a 1-sided alpha level of 0.025 using a Chi-square test. The secondary endpoints will be tested at a 2-sided alpha level of 0.05.

Participants who are randomized but drop out before receiving their randomized treatment (active treatment or sham procedure) will not be considered enrolled in the study. Participants who are unblinded before the 90-day visit due to medical necessity will not be included in the analysis of efficacy endpoints. For long-term follow-up analyses, crossover participants will be analyzed with the active treatment participants.

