2.8.1 Inclusion criteria

Study participants MUST meet all of the following criteria:

- 1. Be \geq 21 years of age.
- 2. Has been diagnosed with chronic nonallergic or allergic rhinitis.
- 3. Have moderate to severe symptoms of rhinorrhea (individual rTNSS symptom rating of 2 or 3), mild to severe symptoms of nasal congestion (individual rTNSS symptom rating of 1, 2, or 3), and a minimum total rTNSS score of 4 (out of 12) at baseline.
- 4. Have an allergy test (by skin prick or intradermal testing or by validated *in vitro* tests for specific Immunoglobin E [IgE]) on file within 12 months of the baseline visit.
- 5. Be an appropriate candidate for bilateral ClariFix treatment performed under local anesthesia.
- 6. Be willing and able to comply with all study elements, as indicated by their written informed consent.

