2.10.3 Baseline visit

The following activities are conducted at the baseline visit:

- 1. Participant completes questionnaires: rTNSS, RQLQ(S), EQ-5D-5L, and Nasal Obstruction Symptom Evaluation (NOSE).
- 2. Record concomitant medications (confirm discontinuation of IB for at least 14 days prior, if applicable).
- 3. Review eligibility criteria; if participant continues to meet eligibility criteria, schedule for randomization and procedure. The study procedure must be scheduled within 7 days of the baseline visit (the procedure can occur on the same day as the baseline visit if all criteria are met).

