2.10.4 Randomization and blinding

Randomization assignments will be generated by in independent statistician using variable block size distribution by site with a 1:1 allocation to active or sham treatment. Randomization will also be stratified by allergy subgroup (allergic, nonallergic). The randomization schedule will be entered into the Medrio electronic data collection (EDC) randomization module. Randomization will occur on the day of the procedure and after all baseline data have been collected and eligibility has been confirmed. All randomized and treated participants will be considered enrolled. Confirmation of randomization assignment from EDC will be printed and filed in the study record.

This is a single-blind study; participants will be blinded to the randomized assignment. To facilitate blinding, control participants will undergo a sham procedure using the ClariFix device without a cryogen cannister. To support blinding, participants will wear blindfolds during the procedure to limit any visual clues that may suggest the treatment assignment. A separate device with a canister held near the participant will be used to provide the sound of the gas release from the cannister. A standardized script for the physician/staff will be used during the procedure to assure blinding. Additionally, local anesthesia regimes will be the same for both treatment groups within each investigational center.

Participants will complete a blinding questionnaire at completion of the procedure and at the 30-day and 90-day follow-up visits to assess the adequacy of the blinding procedures. Upon

completion of their 90-day visit, each participant will be unblinded. Sham control participants will be offered the opportunity to receive active treatment if they wish and still meet eligibility criteria.

Before the 90-day visit, unblinding of participants will only occur when medically necessary. In the event of a device-or procedure-related SAE, the sponsor may authorize the site to unblind the participant in order to adequately assess the event.

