2.11.2 Secondary endpoint assessments

Reflective Total Nasal Symptom Score (rTNSS)

The rTNSS will be collected at screening, baseline, and all follow-up visits. The mean change from baseline in the rTNSS for both treatment groups will be evaluated and compared between treatment groups as a secondary endpoint at the 30-day and 90-day follow-up periods. Additionally, the mean change from baseline will be accessed at all follow-ups for all participants who received active treatment (randomized or crossover).

Rhinoconjunctivitis Quality of Life Questionnaire (RQLQ(S))

The RQLQ(S) is a validated PRO that measures functional impairments due to allergic or non-allergic rhinoconjunctivitis. ^{15,16} The assessment consists of 28 questions related to nose symptoms, eye symptoms, non-eye/nose symptoms, sleep problems, practical problems, activity limitations, and emotional function. Each item is scored from 0 (no impairment) to 6 (severely impaired). An overall score is calculated from the mean of the 28 item responses. Domain scores are the mean of the item scores within that domain. The RQLQ(S) differs from the initial RQLQ in that it standardizes the 3 activities reported for the duration of the study.

The RQLQ(S) will be completed at baseline and all follow-up visits. The mean change from baseline in the RQLQ(S) will be evaluated and compared between treatment groups as a secondary endpoint at the 30-day and 90-day follow-up periods. Additionally, the mean change from baseline will be accessed at all follow-ups for all participants who received active treatment (randomized or crossover).

EuroQOL (EQ-5D-5L)

The EQ-5D-5L is a validated, standardized questionnaire used to evaluate general health-related quality of life. ^{17,18} The questionnaire consists of 5 health dimensions (mobility, self-care, usual activities, pain/discomfort, and anxiety/depression) and a visual analog scale (VAS) to indicate overall health on a scale of 0 to 100. Each health dimension has 5 possible responses: no problems, slight problems, moderate problems, severe problems, or extreme problems. The questionnaire is designed to be self-completed by the participant.

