The EQ-5D-5L will be completed at baseline and all follow-up visits. The mean change from baseline in the EQ-5D-5L will be evaluated and compared between treatment groups as a secondary endpoint at the 30-day and 90-day follow-up periods. Additionally, the mean change from baseline will be accessed at all follow-ups for all participants who received active treatment (randomized or crossover).

Satisfaction questionnaire

The satisfaction questionnaire consists of 3 questions that the participant answers at each follow-up visit. The questions indicate whether the participant is satisfied with the procedure outcome, whether the participant would undergo the procedure again for similar results, and whether the participant would recommend the procedure to family or friends with a similar condition. For each item the participant indicates agreement/disagreement with each statement.

Serious device- or procedure-related adverse events (SAEs)

The rate of serious device- or procedure-related adverse events (SAEs) will be compared between treatment groups through the 90-day follow-up visit (**Section 6**). The parameter of interest is the percent of participants who experience 1 or more device- and/or procedure-related SAEs from the time of the index procedure through the 90-day follow-up.

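### The mean-change comparisons of rTNSS, RQLQ(S) and EQ-5D-5L are at best unadjusted; ANCOVA on baseline score and allergy subgroup would gain precision at no cost

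*Combined protocol and SAP*

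**What the plan says.** Section 2.7 names a test for the primary endpoint (Chi-square, one-sided 0.025). For the rest it gives a level and no method: "The secondary endpoints will be tested at a 2-sided alpha level of 0.05".

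Section 2.11.2 describes the rTNSS comparison: "The mean change from baseline in the rTNSS for both treatment groups will be evaluated and compared between treatment groups as a secondary endpoint". RQLQ(S) and EQ-5D-5L get the same wording, and section 2.3.2 sets the time points at days 30 and 90. None of these places names a model or covariate.

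The material for an adjusted analysis is already planned. Section 2.10.3 collects all three baselines: "Participant completes questionnaires: rTNSS, RQLQ(S), EQ-5D-5L, and Nasal Obstruction Symptom Evaluation (NOSE"). Section 2.10.4 records the allergy stratum: "Randomization will also be stratified by allergy subgroup (allergic, nonallergic").

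The only other sentence on continuous data concerns description: "continuous variables will be summarized with means and standard deviations (normal distributions) or medians and ranges (non-normal distributions"). The protocol points to a separate plan only for other outcomes: "Additional exploratory outcomes will be detailed in the Statistical Analysis Plan".

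**The concern.** These are formal tests with a stated alpha, and the protocol expects the 90-day results to be published as early outcomes (section 11). An unadjusted comparison of mean change and an ANCOVA on the baseline score both estimate a difference in mean change. The text therefore admits both, and the choice could be made after the data are seen.

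Subtracting the baseline is not the same as adjusting for it. A change score fixes the baseline coefficient at 1, whereas ANCOVA estimates it. Unless the best coefficient happens to be 1, the change score carries avoidable noise. At stake are wider intervals on the three main patient-reported measures and a small excess of false positives if the more favourable analysis is reported.

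**Working it through.** **1. The plan's own figure.** Section 2.6 gives responder rates of 73.5% and 45%, one-sided 0.025 and 90% power. With a mean rate of 0.5925,

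n = [1.960·√(2·0.5925·0.4075) + 1.2816·√(0.735·0.265 + 0.45·0.55)]² / 0.285² = (1.3620 + 0.8523)² / 0.081225 = 60.4,

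so 61 per arm and 122 in total, as stated. This is the formula without continuity correction (with it, 68 per arm). It sizes the primary endpoint only; no secondary endpoint has a stated effect, SD or correlation.

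**2. Cost of the change score.** Let r be the baseline SD divided by the follow-up SD, and ρ their correlation. In units of follow-up variance, the change score has variance 1 + r² − 2ρr and ANCOVA has residual variance 1 − ρ². The extra sample needed by the change score is

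(1 + r² − 2ρr)/(1 − ρ²) − 1 = (r − ρ)²/(1 − ρ²).

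This is never negative, and it is zero when r = ρ. All values of r and ρ below are assumed.

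| r | ρ = 0.5 | ρ = 0.7 |
|---|---|---|
| 1.0 | 0.25/0.75 = 33% | 0.09/0.51 = 18% |
| 0.9 | 0.16/0.75 = 21% | 0.04/0.51 = 8% |
| 0.8 | 0.09/0.75 = 12% | 0.01/0.51 = 2% |
| 0.7 | 0.04/0.75 = 5% | 0/0.51 = 0% |

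**3. As power.** Take 61 per arm, two-sided 0.05, r = 1 and an assumed true difference of 0.5 follow-up SD. Power is Φ(0.5/(s·√(2/61)) − 1.96), with s = √(2(1 − ρ)) for change and √(1 − ρ²) for ANCOVA.

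- ρ = 0.5: s = 1.000 and 0.866; power 79% and 89%.
- ρ = 0.7: s = 0.775 and 0.714; power 95% and 97%.

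These are the equal-SD cases, where the gap is widest for these correlations.

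**4. rTNSS under the entry rules.** Entry requires "a minimum total rTNSS score of 4 (out of 12) at baseline", plus minimum rhinorrhea and congestion ratings. This narrows the baseline and lowers r. Four correlated 0-to-3 items were simulated (item correlation 0.2 or 0.4; visit-to-visit persistence 0.4, 0.6 or 0.8; all assumed). The entry rules were applied, and follow-up was calibrated to the responder rates in section 2.6. This gave r of 0.72 to 0.85, ρ of 0.27 to 0.64 and a sample-size penalty of 5 to 26%. With 61 per arm:

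| True effect | Power, change score | Power, ANCOVA | Trials where they disagree on significance |
|---|---|---|---|
| Planned (73.5% vs 45%) | 96–98% | 98–99% | 0.7–3.3% |
| Half (59% vs 45%) | 44–48% | 49–53% | 8–17% |

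**5. Choosing after the fact.** With no treatment effect, taking the smaller p-value of the two methods gave 6.3 to 7.6% false positives in the rTNSS simulation. With simple normal data at correlations of 0.3 to 0.6 it gave 5.7 to 7.4%. Each test alone holds about 5%. The excess shrinks towards nothing as r approaches ρ, because the two analyses then nearly coincide.

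**The case against.** The strongest reply is that little turns on this. The change-score estimate is unbiased under randomisation. For rTNSS at the planned effect both methods have at least 96% power and rarely disagree. The magnitudes rest on assumed SDs and correlations, and RQLQ(S) includes nose symptoms, so the entry rules may narrow its baseline too. At r = ρ = 0.7 the gain is nil. All of this stands, and it limits the size of the point. It does not argue for leaving the method open, since adjusting costs nothing.

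A second reply is that a separate SAP may name the model. It may. The text here assigns that plan only exploratory outcomes, so at the least a cross-reference is missing.

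A third is that the proposed model omits site, the other randomisation factor. In simulated allocations of 128 people to 12 sites, adding site changed the interval width by about +0.8% with no site effect and −1.7% at an assumed intraclass correlation of 0.05. Leaving it out costs little.

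A reader might also infer four stronger things that the documents do not support:

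- **A rank test is also open.** The endpoints are defined as mean change, and the mean-or-median sentence governs summaries only.
- **The result is biased without adjustment.** It is not.
- **The choice of test could swing the SAE conclusion.** Chi-square and Fisher do differ at 4/61 versus 0/61 (p = 0.042 and 0.119), but section 1.2 reports no related SAE in 27 pilot participants. At 3/61 versus 0/61 neither is significant (0.079 and 0.244).
- **The primary test should be stratified by allergy.** Over the 95% interval for the FROST allergy log-odds ratio (−0.98 to 0.96), a Cochran-Mantel-Haenszel test adds only 0.0 to 0.3 points of power. The 61 per arm already implies the uncorrected Z or Chi-square test, and these are equivalent.

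**Conclusion.** The point holds as an improvement available at no cost, not as an error that threatens the trial. On the supplied text the three mean-change comparisons are at best unadjusted. They leave unused a baseline score and an allergy stratum that the trial already collects.

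The gain from ANCOVA is worth about 0 to 33% in sample size, for assumed SD ratios of 0.7 to 1.0 and correlations of 0.5 to 0.7. Fixing the method also removes a choice that would raise false positives to roughly 6 to 8% per comparison. The practical difference is small for rTNSS at the planned effect. It is larger if the effect is about half that, and possibly for RQLQ(S) and EQ-5D-5L, for which the documents give no expected effect. The primary claim and its sample size are untouched. The absence of a named test for satisfaction and for the SAE rate ("The rate of serious device- or procedure-related adverse events (SAEs) will be compared between treatment groups through the 90-day follow-up visit") is a matter of detail.

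**What to change.** State in section 2.7 that change from baseline in rTNSS, in RQLQ(S) and in each reported EQ-5D-5L score is compared between arms at day 30 and at day 90 by ANCOVA. The terms are treatment, the corresponding baseline score and allergy subgroup; report the adjusted mean difference with its 95% CI. Fix this before any 90-day comparison is run. If a separate SAP already specifies this model, cite it in section 2.7 instead.

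Two tidying edits can go in at the same time: name a test for satisfaction and one for the SAE rate, and use one name in sections 2.5 and 2.7 for the uncorrected Z/Chi-square primary test. The primary test itself need not change.

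The cost is wording only. No visit, measurement, stratum or participant is added.

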2.3.2 Secondary endpoints

The following secondary endpoints will compare the active treatment group with the sham-control group at 30-day and 90-day follow-ups:

- Mean change from baseline in rTNSS score
- Mean change from baseline in Standardized Rhinoconjunctivitis Quality of Life Questionnaire (RQLQ(S)) score
- Mean change from baseline in EuroQol 5-dimension survey (EQ-5D-5L) scores
- Percent of patient satisfaction at follow-up
- Rate of serious device- or procedure-related adverse events (SAEs)

The following secondary endpoints will be assessed at all follow-ups for all participants who receive active treatment (randomized or crossover):

- The percentage of responders
- The mean change from baseline in rTNSS score
- The mean change from baseline in RQLQ(S) score
- Mean change from baseline in EQ-5D-5L scores
- Percent of patient satisfaction at follow-up

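### Section 2.7 tests about nine between-arm secondary comparisons at two-sided 0.05 with no order, gate on the primary or adjustment, so the familywise error is well above 5%

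*Combined protocol and SAP*

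**What the plan says.** Section 2.7 (Data analyses) sets two significance levels. For the primary: "The primary efficacy endpoint will be tested at a 1-sided alpha level of 0.025 using a Chi-square test". For the rest: "The secondary endpoints will be tested at a 2-sided alpha level of 0.05".

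Section 2.3.2 introduces its first list with "The following secondary endpoints will compare the active treatment group with the sham-control group at 30-day and 90-day follow-ups". Five endpoints follow:

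- rTNSS, as a mean change
- RQLQ(S), as a mean change
- EQ-5D-5L, where the wording is plural: "Mean change from baseline in EuroQol 5-dimension survey (EQ-5D-5L) scores"
- patient satisfaction
- related serious adverse events (SAEs).

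Section 2.11.2 gives detail that affects the count. On satisfaction: "The satisfaction questionnaire consists of 3 questions that the participant answers at each follow-up visit". No item or composite is named as the one to be tested. On EQ-5D-5L it describes five dimensions and a visual analog scale (VAS) without saying which score is compared. On safety: "The rate of serious device- or procedure-related adverse events (SAEs) will be compared between treatment groups through the 90-day follow-up visit". It then defines the parameter as the percentage of participants with at least one such event from the index procedure to day 90, which is a single comparison.

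The supplied text has no testing sequence, no condition on the primary result, no multiplicity adjustment, and no key secondary endpoint or lead visit. The plan summary and section 2.3.3 mention a Statistical Analysis Plan, but only for exploratory outcomes.

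**The concern.** The plan does not call the secondary endpoints descriptive. It gives them a test level, which is a decision rule. Read as written, each comparison can be declared significant at 0.05 whatever the others show and whether or not the primary succeeds.

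The size of the family is also open. EQ-5D-5L could mean one score or two, and satisfaction could mean one item or three. Both choices could be made after results are known.

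What is at stake is publication. Section 2.2.2 makes support for peer-reviewed papers a secondary objective, and section 11 allows outcomes through 90 days to be published separately. The primary could miss while one of eight or so patient-reported comparisons is reported as a significant result of a prespecified test. Nothing in the text prevents this.

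**Working it through.** **1. The plan's own figure.** The documents give no familywise error rate for the secondary endpoints. The figure that can be reproduced is the primary sample size (section 2.6): response rates 73.5% and 45%, 90% power, one-sided 0.025. With pooled variance and p̄ = (0.735 + 0.45)/2 = 0.5925:

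n per arm = [1.960 × √(2 × 0.5925 × 0.4075) + 1.282 × √(0.735 × 0.265 + 0.45 × 0.55)]² / 0.285² = [1.362 + 0.852]² / 0.0812 = 60.4, rounded up to 61, so 122 in total.

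This matches the plan. The primary is one test using its full alpha, so nothing below changes its error rate or power.

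**2. Counting the between-arm secondary tests** (sections 2.3.2 and 2.11.2).

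| Endpoint | Lean count | Expanded count |
|---|---|---|
| rTNSS change, 2 visits | 2 | 2 |
| RQLQ(S) change, 2 visits | 2 | 2 |
| EQ-5D-5L, 2 visits | 2 (one score) | 4 (index and VAS) |
| Satisfaction, 2 visits | 2 (one item) | 6 (three items) |
| Related SAEs through day 90 | 1 | 1 |
| **Total** | **9** | **15** |

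The second list in section 2.3.2, for everyone who receives active treatment, compares no randomized arms and is not counted.

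**3. Independent tests, all secondary nulls true.** Chance of at least one false positive = 1 − 0.95^k. Chance of at least one favoring active = 1 − 0.975^k.

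| k | Any false positive | Favoring active |
|---|---|---|
| 8 (no SAE test) | 33.7% | 18.3% |
| 9 | 37.0% | 20.4% |
| 15 | 53.7% | 31.6% |

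**4. Correlated tests.** Scores from the same participants are correlated. The documents give no correlations, so these are assumptions. For 9 normal test statistics with one common correlation:

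| Assumed correlation | Any false positive | Favoring active |
|---|---|---|
| 0.3 | 32.6% | 16.5% |
| 0.5 | 26.9% | 13.5% |
| 0.7 | 20.2% | 10.1% |

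A more structured model of the four patient-reported outcomes at two visits, without the SAE test, gives similar values: 29.7% (between-endpoint 0.3, between-visit 0.5), 26.9% (0.5, 0.5) and 20.9% (0.7, 0.7).

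**5. The SAE test.** With 64 per arm and Fisher's exact test (an assumption, since the plan names no test for this endpoint), the actual size is below 0.4% for true rates up to 3%. This comparison adds almost nothing, so the effective family is closer to 8 than 9.

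**6. After the fix.** A fixed sequence holds the familywise error of the tests in it to at most 5%. With the gate, if the primary null is also true, the chance of any secondary claim is at most 2.5%, the chance that the gate opens. For comparison, Bonferroni over 9 tests would need 0.05/9 = 0.0056 per test.

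**The case against.** The strongest reply is that the plan makes no confirmatory claim for these endpoints. Section 2.5 writes a superiority hypothesis only for the 90-day responder rate, so a secondary p-value cannot rescue a failed primary. Section 4.1 says the device is already cleared and used on-label, and no label claim is mentioned. The error rates also assume that every secondary null is true. Mean rTNSS change uses the primary's own instrument, so if the primary effect is real, that null is unlikely to hold.

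Much of this stands, and it limits how serious the point is. It does not remove it: the text neither labels the secondary results nominal nor restricts their use, and it sets a level at which they are tested.

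Three stronger readings are tempting and are not supported:

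- **That a false secondary claim is likely.** The lean count stays below 40% even with independent tests and all nulls true. Only the expanded count passes 50%, and only if 15 outcomes from the same participants are treated as independent. Section 2.11.2 describes three satisfaction questions but does not say that each is tested.
- **That every endpoint is tested at two visits.** The list heading in section 2.3.2 suggests this, but section 2.11.2 defines the SAE rate as one cumulative comparison. Counting it twice gives 16 tests and 1 − 0.95^16 = 56%, which should not be used.
- **That the primary conclusion is weakened.** It is a single test at one-sided 0.025 and is unaffected.

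A separate analysis plan might deal with multiplicity. The absence is claimed only for the supplied text.

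**Conclusion.** The point holds as a should-fix item. Following section 2.7 as written gives a chance of at least one false significant secondary result of 37% for 9 independent tests, and roughly 20% to 33% at assumed common correlations of 0.7 to 0.3. About half of those results would favor active: 20.4% in the independent case and 10% to 17% in the correlated cases. These figures rest on all secondary nulls being true, on correlations that the documents do not supply, and on a count of 9 that includes an SAE test contributing very little. Across these counts and correlations the rate is several times 5%. The consequence is confined to how secondary results may be reported.

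**What to change.** In section 2.7, replace the single sentence on secondary testing with a gated fixed sequence. If the primary is met, test in order, each at two-sided 0.05, and stop at the first non-significant result. One possible order is:

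1. 90-day mean rTNSS change
2. 90-day RQLQ(S) change
3. one named satisfaction item
4. one named EQ-5D-5L score.

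The order is the sponsor's choice. It should be fixed in a dated amendment before anyone reviews outcome data by arm. Fixing it before unblinding would not be a sufficient safeguard: under section 2.10.4 only participants are blinded and each is told the assignment at the 90-day visit, while section 2.11 has sponsor staff reviewing data throughout.

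Report the 30-day comparisons and the SAE comparison with 95% confidence intervals and nominal p-values only.

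If the sponsor wants no hierarchy, a sentence stating that all secondary p-values are nominal and support no significance claim is enough.

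Cost: short wording changes to sections 2.3.2 and 2.7, no extra participants and no loss of primary power. The downside is that an endpoint ranked below a failed one, and all 30-day comparisons, could not be claimed as significant.
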